16. Two pretreatment 6MWTs are required before the first administration of study drug, with a minimum of 4 days in between the two tests. The first Screening 6MWT is required to be performed between Days -28 and -5, at least 4 days prior to the second Screening 6MWT, which should be performed within 2 days prior to Month 1-Day 1 (i.e., on Day -2 or Day -1).

17. The postbaseline 6MWTs may be administered on the same calendar day that study drug is administered (i.e., Months 3, 6, 9, 12) as long as the NT-proBNP sample is drawn before conducting the 6MWT and the 6MWT is completed before initiation of the study drug infusion.
18. Perform echocardiogram locally; **Screening:** If an echocardiogram was conducted within 90 days prior to Screening Day -28, it does not need to be repeated during Screening and the previous result may be used for eligibility; however, to be eligible for the additional cardiac imaging analysis, the subject must have had a 4-chamber view, 2-dimensional echocardiogram with Doppler. **Month 12:** may be conducted within 10 days before Day 1; **EOS/ETD:** repeat if not performed within 60 days prior to visit.
19. **Months 1, 3, 6, 9, 12:** perform ECGs centrally within 30 minutes before dosing and within 15 minutes after EOI.
20. Hematology and chemistry per [Appendix 11](#).
21. Collect PT/INR and PTT at each time point. At Screening, EOS/ETD, and as clinically indicated, collect citrated plasma samples for freezing and for potential analysis of coagulation indices at a later date; these analyses may include, but may not be limited to, the indices listed in [Appendix 12](#).
22. Inflammatory biomarkers per [Appendix 11](#).
23. Collect additional samples as clinically indicated, such as when significant toxicity occurs per [Section 5.4.2](#).
24. All laboratory tests to be done centrally, unless otherwise noted. Please refer to Laboratory Manual for details.
25. Pregnancy tests for WOCBP as follows: **Screening:** serum test (central) within 28 days before Month 1-Day 1; **Month 1:** serum test (local) within 24 hours before Month 1-Day 1; **Months 2-12:** serum test (local) preinfusion; **EOS/ETD:** serum test (central); **90 (±5) days after the last study drug administration:** serum test (local).
26. The serum and urine PEP must be conducted before the NEOD001 infusion, if being performed on the same calendar day.
27. Per [Appendix 11](#).

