6.1.2 Treatment Visits

Study visits will occur every 28 days based on scheduling from Month 1-Day 1. A ± 5 -day window is allowed for visits starting after Month 1. Subjects may receive up to 12 infusions of study drug; a minimum of 21 days between doses is required.

The predose assessments for each visit may be performed within the 3 days before the visit unless otherwise specified. Although central laboratory assessments will be performed each month for study analysis, local laboratory assessments may be performed for subject management when necessary for obtaining results on a more immediate basis. Results will be reviewed prior to dosing at each month's Day 1 visit to confirm that continued dosing is appropriate.

Subjects who present with symptomatic orthostatic hypotension and/or systolic BP <85 mmHg, which in the medical judgment of the Investigator would interfere with the subject's ability to safely receive treatment, will have study drug withheld until the next scheduled monthly administration, but should still have all other study visit assessments completed. If study drug is withheld and subsequently rescheduled, central laboratory assessments required for that visit will need to be repeated if they were drawn >7 days prior to the rescheduled dosing date. However, a symptom-directed physical exam and vital signs need to be repeated prior to each dosing.

6.1.2.1 Month 1-Day 1

Prior to Study Drug Infusion:

The following assessments will be done prior to dosing on Month 1-Day 1:

- Concomitant medications/therapies
- Assessment of AEs
- Directed physical examination - including weight and examination of the following: general appearance; head, ears, eyes, nose, and throat; neck; skin; cardiovascular system; respiratory system; gastrointestinal system; and nervous system. The components of the physical exam will be as clinically indicated; however, the following should be assessed: macroglossia, submandibular nodes/fullness, adenopathy, ecchymoses, liver/spleen size (palpable +/-), ascites (+/-), and edema (which should be quantified on a scale of 0-4).
- Vital signs including HR, BP, RR, and body temperature (per [Section 6.6.1.2](#)) – within 30 minutes before dosing, after subject has been at rest ≥ 5 minutes; assess in same position for all time points
- ECOG PS ([Appendix 7](#))
- NYHA class ([Appendix 8](#))
- NIS-LL ([Appendix 5](#)) and VASPI ([Appendix 6](#))

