6.6 Methods of Assessment

6.6.1 Safety

6.6.1.1 *Clinical Laboratory Evaluations*

A central laboratory will be used for this study for analysis of hematology, chemistry (including amylase), coagulation, inflammatory biomarkers, cardiac biomarkers, serum free light chains, serum IFE/PEP, urinalyses, and 24-hour urine collection for urine IFE/PEP and urine protein excretion. Central and local pregnancy testing will be conducted as shown in [Table 1](#).

Local laboratory results may be obtained at the Investigator's discretion for subject management when necessary for obtaining results on a more immediate basis. Results will be reviewed prior to dosing at each month's Day 1 visit to confirm that continued dosing is appropriate. Results from local laboratory tests will not be collected in the eCRFs or the clinical database.

Citrated plasma samples will be collected and frozen for potential analysis of coagulation indices at a later date. These analyses may include but may not be limited to the indices listed in [Appendix 12](#).

Urine samples will be collected and frozen for potential analysis of renal biomarkers at a later date (see [Appendix 11](#)). It is important that the sample be taken before exercising and at approximately the same time for each collection; therefore, the first morning void is recommended.

The 24-hour urine IFE/PEP and 24-hour urine protein excretion tests will be performed using the same 24-hour urine collection sample when required at the same visit. Details regarding the 24-hour urine sample collection will be provided in the Laboratory Manual.

A bioanalytical laboratory will be used for the analysis of NEOD001 and anti-NEOD001 samples, as well as for the storage of serum samples for future correlative testing ([Sections 6.6.3](#) and [6.6.4](#)).

One or more laboratories will be used for mass spectrometry of tissue samples, immunoelectron microscopy, gene sequencing, and/or ^{99m}Tc scintigraphy, which are required for subjects who meet Inclusion Criterion #3.

Details for the processing of laboratory specimens will be provided in the Laboratory Manual.

6.6.1.2 *Vital Signs*

Predose vital signs should be assessed within 30 minutes before dosing. Vital signs should be measured after the subject has been at rest ≥ 5 minutes. Within a single visit, assess in the same position for all time points.

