Appendix 4 Organ Response and Progression Criteria

Organ	Response	Progression
Heart/Cardiac ^a	NT-proBNP response (>30% and >300 ng/L decrease in subjects with baseline NT-proBNP \geq 650 ng/L) OR NYHA class response (\geq 2 class decrease in subjects with baseline NYHA class III or IV)	NT-proBNP progression (>30% and >300 ng/L increase) ^b
Kidney/Renal ^c	\geq 30% decrease in proteinuria or drop of proteinuria below 0.5 g/24 hours in the absence of renal progression	\geq 25% decrease in eGFR
Peripheral Nerve ^d	NIS-LL increase from baseline of <2 points	NIS-LL increase from baseline of \geq 2 points
Liver/Hepatic ^a	50% decrease in abnormal ALP value	\geq 50% increase in ALP above the lowest value

Abbreviations: ALP = alkaline phosphatase; eGFR = estimated glomerular filtration rate; NIS-LL = Neuropathy Impairment Score–Lower Limbs; NT-proBNP = N-terminal pro-brain natriuretic peptide; NYHA = New York Heart Association.

- a Modified from Table 2 in [Comenzo et al, 2012](#). In addition to the progression criteria listed above, the investigators will use their best clinical judgment in circumstances that do not meet the specifically referenced criteria above in assessing the progression. A repeated assessment at an interval that is determined by the investigator is required to confirm the progression.
- b Subjects with progressively worsening renal function cannot be scored for NT-proBNP progression.
- c [Palladini et al, 2014](#).
- d [Coelho et al, 2012](#).

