8.10.7.2. Cardiac Progression-Free Survival

Cardiac progression is defined as NT-proBNP progression of >30% increase and >300 ng/L increase or death. Cardiac progression will not be evaluated in the presence of renal progression, defined as an eGFR of < 30 mL/min/1.73 m², according to [Comenzo 2012 \(Appendix 2\)](#).

Progression-free survival is defined as the time from first infusion of study drug to the earliest of:

- first documented date of disease progression (as defined by NT-proBNP [Section 2.3.4.1.1]) or
- withdrawal from treatment or study due to organ (cardiac) progression or
- death on the study or
- death following withdrawal from treatment due to any cause.

Progression-free survival will be calculated in days as the earliest of the above dates (disease progression or death) minus the date of first infusion of study drug plus 1.

Subjects who are alive with no documented progression prior to the end of the study will be censored at the earliest of their date of the first assessment that meets renal progression (defined as an eGFR of < 30 mL/min/1.73 m²), date of the last NT-proBNP measurement, or date they withdraw consent or are lost to follow-up.

NEOD001 will be compared to placebo using the log rank test stratified by the randomization stratification factors. KM estimates of the distribution of the time-to-event will be tabulated and graphed by treatment group. The tabulation will include the KM estimate of the medians, 25th and 75th percentiles, and corresponding 95% CIs, if estimable. The tabular and graphical summaries will include the at-risk counts for every visit. The number and percent of subjects

censored and with events will be presented overall and for each visit, using last day of the visit window. The hazard ratio and 95% CI will be determined based on a Cox regression model stratified by randomization strata to estimate the magnitude of the effect.

In addition, a sensitivity analysis will be performed counting death or progression without subsequent response as an event.

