8.10.7.3. Duration of Cardiac Response

Cardiac response is defined as >30% decrease and >300 ng/L decrease in NT-proBNP from baseline.

Duration of cardiac response is defined for subjects experiencing response as the time from the earliest cardiac response to the first documented date of disease progression, as defined by NT-proBNP progression of >30% increase and >300 ng/L increase. Subjects without response will be excluded from this analysis.

Duration of Cardiac Response will be calculated in days as the date of disease progression minus the date of first response plus 1.

Subjects will be censored at their date of the last NT-proBNP measurement if they complete the study or discontinue with no documented progression.

NEOD001 will be compared to placebo using the log rank test stratified by the randomization stratification factors. KM estimates of the distribution of the time-to-event will be tabulated and graphed by treatment group. The tabulation will include the summary statistics as described for continuous variables in Section 4.1, KM estimate of the medians, 25th and 75th percentiles, and corresponding 95% CIs, if estimable. The tabular and graphical summaries will include the at-risk counts for every visit. The number and percent of subjects censored and with events will be presented overall and for each visit, using last day of the visit window. The hazard ratio and 95% CI will be determined based on a Cox regression model stratified by randomization strata to estimate the magnitude of the effect.

In addition, a sensitivity analysis will be performed for subjects experiencing response as the time from the earliest cardiac response to the first documented date of disease progression without subsequent response.

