10. CHANGES TO PROTOCOL PLANNED ANALYSES

Per Protocol A3, Section 8.3.4: “All exploratory quantitative endpoints, except the 6MWT.... will be analyzed in the same manner described for the SF-36v2...”. The exploratory analyses of LVEF are performed per Section 8.10.1.2 of this SAP.

Appendix 4 of the protocol, footnotes a and b, state “In addition to the progression criteria listed above, the investigators will use their best clinical judgment in circumstances that do not meet the specifically referenced criteria above in assessing the progression. A repeated assessment at an interval that is determined by the investigator is required to confirm the progression.” and “Subjects with progressively worsening renal function cannot be scored for NT-proBNP progression.” Repeat assessments were only done using local laboratories and therefore not included in the central laboratory data for inclusion in analyses. In addition, per the SAP renal progression is not considered for the primary endpoint analyses and is only included as a sensitivity analysis.

Renal endpoints other than renal response will be repeated for the ITT population.

The Safety Population was updated to use treatment received for all subjects instead of randomized treatment.

The following endpoints were removed:

- Time to eGFR ≤ 15 mL/min/1.73 m² (Chronic Kidney Stage 5)
- Time to doubling of creatinine
- Time to peripheral neuropathy organ progression
- Time to peripheral neuropathy organ response
- Time to hepatic organ progression
- Time to hepatic organ response
- Hematologic response at each visit
- Hematologic best response through 3, 6, 9, and 12 months of treatment
- Mayo Clinic Stage including any subgroup analyses
- Peripheral neuropathy best response through 3, 6, 9, and 12 months of treatment

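### The SAP drops the protocol's confirmation of progression and puts no rule based on the monthly central NT-proBNP readings in its place, so the exploratory cardiac progression endpoints count the first single qualifying reading

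*SAP*

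**What the plan says.** **Confirmation rule.** Protocol Appendix 4, footnote a, is attached to the cardiac and hepatic rows and ends: "A repeated assessment at an interval that is determined by the investigator is required to confirm the progression".

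**Departure.** SAP Section 10 cites that footnote among the changes to planned analyses and explains: "Repeat assessments were only done using local laboratories and therefore not included in the central laboratory data for inclusion in analyses". No other confirmation rule follows. SAP Appendix 2 repeats the thresholds without the confirmation sentence.

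**Data available.** Local results cannot be recovered. Protocol 6.6.1.1 says: "Results from local laboratory tests will not be collected in the eCRFs or the clinical database". Central results are plentiful. Protocol 6.1.2 says: "Although central laboratory assessments will be performed each month for study analysis", and a Table 1 footnote adds: "All laboratory tests to be done centrally, unless otherwise noted". Table 1 marks NT-proBNP at every treatment visit and at EOS/ETD.

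**Use in the analysis.** SAP 8.10.7.2 says: "Cardiac progression is defined as NT-proBNP progression of >30% increase and >300 ng/L increase or death". The PFS event is the "first documented date of disease progression", unless death or withdrawal for cardiac progression comes first. SAP 8.10.7.3 measures duration of response as "the time from the earliest cardiac response to the first documented date of disease progression". SAP 8.10.7.4 likewise takes the first assessment that shows progression, both for cardiac progression and for the cardiac-or-renal composite.

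**Existing safeguard.** For PFS and duration of response, a sensitivity analysis counts a progression only if no response follows it. None is listed for the endpoints in 8.10.7.4.

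**The concern.** The reason in SAP Section 10 explains why the local retests cannot be used. It does not explain why there is no confirmation at all. The protocol leaves the repeat interval open, and a scheduled central value about 28 days later is a repeat assessment that is already in the analysis data.

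Without confirmation, each subject has up to 12 chances to cross a threshold measured against a single baseline value (SAP 2.2.7). A chance high reading that falls back the next month becomes a permanent event. Such errors are blind to treatment arm, so they would not be expected to favour either arm. They add events unrelated to treatment, which tends to move the hazard ratio toward 1 and to shorten apparent time to progression in both arms.

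**Working it through.** **1. The plan's own figure.** The documents give no power, event count or error rate for any progression endpoint. The only figure to reproduce is the primary-endpoint power: 50% vs 22.5%, two-sided α = 0.05, 65 per arm. With the pooled mean rate (0.50 + 0.225)/2 = 0.3625,

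power = Φ{[0.275 − 1.96·√(2·0.3625·0.6375/n)] / √[(0.50·0.50 + 0.225·0.775)/n]}

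This gives 91.3% at n = 65 (stated 91%) and 82.6% at n = 50 (stated >80%). Neither changes under the fix, because SAP 2.3.1 counts stable and progression alike as non-response.

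**2. Readings available.** Months 2 to 12 give 11 post-baseline central values and EOS gives one more, 12 in all. Every value except the last has a later central value that could confirm it.

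**3. False progression in a truly stable subject.** *From the documents:* progression is a rise of >30% and >300 ng/L over one baseline reading; baseline eligibility is 650 to 5000 pg/mL. *Assumed:* independent lognormal error with within-subject log SD s, and true level log-uniform over the eligible range. There were 200,000 simulated subjects.

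Hand check for one reading, using the 30% condition alone (the 300 ng/L condition binds only for baselines below 300/0.30 = 1000): P = Φ(−ln 1.3 / (s√2)). At s = 0.10 this is Φ(−0.262/0.141) = Φ(−1.86), about 3%. At s = 0.20 it is Φ(−0.93), about 18%. Over 12 readings that share one baseline:

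| Assumed log SD | Single reading | SAP sensitivity rule (no later response) | Two consecutive readings |
|---|---|---|---|
| 0.05 | 0.1% | 0.1% | 0.0% |
| 0.10 | 16% | 16% | 3% |
| 0.15 | 42% | 41% | 13% |
| 0.20 | 58% | 53% | 24% |

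The SAP's sensitivity rule removes almost nothing at 0.15 or below. A later response needs a fall of >30% and >300 ng/L below baseline, so a spike that merely returns to baseline still counts.

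**4. Share due to baseline error.** At s = 0.10, an error-free baseline alone would cut the single-reading rate from 16% to about 4%. At s = 0.20 this no longer holds. Confirmation does not repair a low baseline reading, which is why 24% remains at s = 0.20.

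**5. Illustration of dilution.** Assume 40% true 12-month progression on placebo, a true hazard ratio of 0.50, and true progression as a 1.8-fold rise. None of these is in the documents.

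| Assumed log SD | Estimated HR, single | Estimated HR, confirmed | False share of placebo events, single | False share, confirmed |
|---|---|---|---|---|
| 0.10 | 0.64 | 0.54 | 26% | 8% |
| 0.15 | 0.78 | 0.63 | 54% | 28% |
| 0.20 | 0.85 | 0.71 | 66% | 44% |

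**6. Three-category best response.** SAP 2.3.1 takes the most favourable category over all visits, so a subject with complete data is a best-response progressor only if every reading is progression. In the no-change model this happens in 0.005%, 0.09% and 0.29% of subjects at s = 0.10, 0.15 and 0.20.

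**The case against.** **The departure is disclosed and its factual basis is right.** Both are true. Local results are not collected, and SAP Section 10 states the change openly. What stands against the SAP is narrower: it offers no substitute, although one was available.

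**The protocol's rule may not cover this case.** The confirmation sentence directly follows one about investigator judgement in cases outside the listed criteria, so it could be read as limited to those. The interval was also the investigator's choice, not the next visit. A central two-reading rule would therefore be a replacement, not a restoration. However, SAP Section 10 cites the sentence without that limit and treats dropping it as a change to the planned analyses.

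**The rates depend on an assumption.** They do. At a log SD of 0.05 the problem disappears. They also describe stable subjects. For duration of response, a subject whose level has truly fallen is further from the progression threshold, so the effect there should be smaller.

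**The SAP already has a sensitivity analysis.** It does some work at high variability (58% to 53% at 0.20), little or none below that, and it does not extend to 8.10.7.4.

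**Nothing confirmatory depends on it.** Correct, and this limits the weight of the point.

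**Conclusion.** The point holds for the exploratory cardiac progression endpoints in SAP 8.10.7.2 to 8.10.7.4. A required confirmation step was dropped, no replacement was set, and the data for one are collected every month. If within-subject log SD is 0.10 to 0.20, about 16 to 58% of truly stable subjects would be called progressors on a single reading, against 3 to 24% on two. At 0.05 the figures are 0.1% and 0%. These results rest on independent errors, one noisy baseline and 12 complete readings.

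Two stronger readings are tempting, and the documents do not support them:

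- *Most progression events are false.* That share needs both the within-subject variability and the true progression rate, and the documents give neither. In the illustration it passes one half at 0.15 but not at 0.10.
- *The primary or three-category results are compromised.* The primary comparison is response against non-response, no key secondary endpoint uses progression, and one spike cannot make a best-response progressor. The by-visit three-category tables do use single readings, but they are snapshots by design.

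**What to change.** In SAP 8.10.7.2 to 8.10.7.4:

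- Define NT-proBNP progression as the threshold met at two consecutive available central readings, dated at the first.
- Count an unconfirmed qualifying reading if the subject dies before the next reading.
- State how a qualifying last reading is handled (EOS/ETD, withdrawal, loss to follow-up), for example censored in the main analysis and counted in the sensitivity analysis.
- Leave the existing events for death and for withdrawal or discontinuation due to progression as they are. The renal component of the composite also stays unchanged.
- Keep single-reading progression as a sensitivity analysis for all four endpoints, including those in 8.10.7.4.

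In SAP Section 10, say that the next central reading replaces the local repeat. Section 8.7.1 needs no change for best response.

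The cost is SAP text, programming and somewhat fewer events. No visit, sample or assay is added. Error in the single baseline reading remains and should be acknowledged when these endpoints are reported.

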12. APPENDICES

APPENDIX 1. HEMATOLOGIC RESPONSE AND PROGRESSION CRITERIA

Response Subcategory	Response Criteria
Complete Response (CR)	Normalization of free light chain levels and ratio, negative serum and urine immunofixation
Very Good Partial Response (VGPR)*	Reduction in the dFLC to <40 mg/L (<4.0 mg/dL)
Partial Response (PR)*	A greater than 50% reduction in the dFLC
No Response (NR)	Less than a PR
Progression	From CR: any detectable monoclonal protein or abnormal free light chain ratio (light chain must double)
	From PR, 50% increase in serum M protein to > 0.5 g/dL or 50% increase in urine M protein to > 200 mg/day (a visible peak must be present) or free light chain increase of 50% to > 10 mg/dL (100 mg/L)

Abbreviations: dFLC = difference between involved and uninvolved free light chains.

*Only applicable for subjects who had dFLC > 50 mg/L (5 mg/dL) prior to treatment.

Source: [Comenzo 2012](#).

